Participants will be followed for safety and efficacy as per schedule of activities and will remain on study treatment until development of distant metastases as assessed by investigators or the development of unacceptable toxicity or the end of study defined as metastasis-free survival (MFS) events observed in approximately 60% of the study population or 3 years after the final analysis for the primary endpoint (TTPP), whichever comes first.

All participants will be monitored for safety during the Screening and Treatment Phases, and for up to 30 days after the last dose of study treatment. An End-of-Treatment (EoT) Visit will occur approximately 30 days of the last dose of study treatment. The Posttreatment Follow-up Phase will begin after the EoT visit. For participants entering Posttreatment Follow-up Phase with evidence of distant metastasis, they will be contacted every 4 months (± 7 days) to obtain survival status, recording of development of symptomatic progression, initiation of any new systemic anticancer therapies until death, withdrawal of consent for study participation, or termination of the study. For participants entering Posttreatment Follow-up Phase without evidence of distant metastasis, Posttreatment Follow-up visits including disease assessment (computed tomography [CT] or magnetic resonance imaging [MRI] plus bone scans) will continue every 16 weeks (± 7 days) until the documentation of disease progression, then participants will be contacted every 4 months (± 7 days) to obtain survival status, recording of development of symptomatic progression, initiation of any new systemic anticancer therapies until death, withdrawal of consent for study participation, or termination of the study.

An Independent Data Monitoring Committee (IDMC) will be commissioned for this study to review the efficacy and safety results of final analysis. The IDMC will consist of at least 1 medical oncologist or urologist or both and at least 1 statistician.

NUMBER OF PARTICIPANTS

A target of 75 Chinese male participants will be randomly assigned in a 2:1 ratio in this study to receive apalutamide or matching placebo with ADT.

INTERVENTION GROUPS AND DURATION

Each treatment cycle will consist of 28 days. Participants will be randomly assigned in a 2:1 ratio:

- Investigational group will receive apalutamide 240 mg (4×60 mg tablets) daily.

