6.5.2. Prohibited Therapy

Concurrent enrollment in another investigational drug or device study is prohibited during the Treatment Phase.

As a class effect, AR antagonists have been associated with seizures due to an off-target mechanism of action (gamma amino butyric acid chloride channel inhibition). Drugs known to lower the seizure threshold or cause seizures are prohibited and a representative list is included below:

- Atypical antipsychotics (eg, clozapine, olanzapine, risperidone, ziprasidone)
- Bupropion
- Lithium
- Meperidine (pethidine)
- Phenothiazine antipsychotics (eg, chlorpromazine, mesoridazine, thioridazine)
- Tricyclic antidepressants (eg, amitriptyline, desipramine, doxepin, imipramine, maprotiline, mirtazapine)
- Aminophylline/theophylline.

The following medications are prohibited while on study until the End-of-Treatment Visit or 30 days after last dose of study drug. The sponsor must be notified in advance (or as soon as possible thereafter) of any instances in which prohibited therapies are administered. Chemotherapeutic, biologic, or other agents with anti-tumor effect against PC.

- Anti-androgens (except as prescribed in the protocol)
- 5-α reductase inhibitors
- Estrogens
- Progestational agents (eg, cyproterone acetate)
- Androgens
- Oral ketoconazole
- Spironolactone
- Bone targeted agents indicated for the treatment of metastatic PC (bisphosphonates or denosumab) are prohibited (NOTE: bone targeted agents indicated for osteoporosis are allowed).

The sponsor must be notified in advance (or as soon as possible thereafter) of any instances in which prohibited therapies are administered.

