7. DISCONTINUATION OF STUDY INTERVENTION AND PARTICIPANT DISCONTINUATION/WITHDRAWAL

7.1. Discontinuation of Study Intervention

Discontinuing treatment will not result in an automatic withdrawal from the study. Participants who discontinue treatment, but do not withdraw consent, should complete the EoT Visit within 30 days of the last dose of study drug and continue the scheduled assessments according to the Posttreatment Follow-up Phase in the Schedule of Activities (SoA).

A participant's study intervention must be discontinued if:

- Documented distant metastases
- The investigator believes that for safety reasons or tolerability reasons (eg, AE) it is in the best interest of the participant to discontinue study intervention
- Initiation of any subsequent prostate anticancer therapy or procedure not specified in the protocol during treatment phases
- Seizure of any grade or Grade 4 neurotoxicity (see Section 6.6);
- Other study drug toxicity (see Section 6.6)
- Withdrawal of consent for continued treatment.

All participants discontinuing study treatment will enter the Posttreatment Follow-up Phase. For participants entering Posttreatment Follow-up Phase with evidence of distant metastasis, they will be followed for survival status, the development of symptomatic progression, initiation of any new systemic anticancer therapies until death, withdrawal of consent for study participation, or termination of the study (every 4 months ± 7 days via clinic visit, telephone contact or an alternative contact method per institution policy/practice), whichever comes first. In addition, if participants discontinued study treatment prior to documented disease progression (distant metastases), CT of the chest, abdomen, and pelvis, or MRI, plus bone scan will be obtained and evaluated for disease progression in Posttreatment Follow-up visits (every 16 weeks ± 7 days), until documentation of disease progression, then participants will be contacted every 4 months (± 7 days) to obtain survival status, recording of development of symptomatic progression, initiation of any new systemic anticancer therapies until death, withdrawal of consent for study participation, or termination of the study.

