9.3. Statistical Analyses

9.3.1. Efficacy Analyses

All continuous variables will be summarized using number of participants (n), mean, standard deviation (SD), median, minimum, and maximum. Discrete variables will be summarized with n and percent. All efficacy endpoints will be analyzed using the ITT Population. Kaplan-Meier method and Cox model, including stratification factor at baseline, will be used to estimate the time-to-event variables and to obtain the HR along with the associated confidence intervals (CIs). Stratified log-rank test will be used as the primary analysis method to test the treatment effect for time-to-event variables. A participant without an event at the time of the analysis will be censored at the last known date the participant did not have a documented record of the corresponding event. Detailed censoring rules will be provided in the SAP. Response rate variable, ie, PSA response rate, will be evaluated using the Mantel-Haenszel test or the exact test if the frequencies are small. The stratification variable will be PSADT (>6 months vs ≤6 months) as documented in the IWRS.

The final analysis of TTPP will be performed at approximately 5 months after last participant receiving the first dose. TTPP will be tested using Stratified log-rank test, stratified by PSADT (>6 months vs ≤6 months), at a 2-tailed significance level of 0.05. The TTPP for control arm will be censored at the date of treatment switching for participants who switched treatment and had not PSA progressed at that time. For participants who received anticancer subsequent therapy before documented PSA progression, the TTPP will be censored at the last date of PSA assessment prior to the start of subsequent therapy. Kaplan-Meier method will be used to estimate the median TTPP, as well as the PSA progression-free rate at selected timepoints, and their 95% CIs. The estimation of HR and its 95% CI will be based on the stratified Cox proportional-hazard model. Non-stratified log-rank tests will also be provided as sensitivity analysis.

The analyses for exploratory time-to-event variables (MFS, OS, and time to symptomatic progression) will be performed descriptively, considering the early cross-over of control arm and the expected long medians for apalutamide arm suggested by study ARN-509-003 (SPARTAN), for participants who randomized to apalutamide arm.²

The MRU data may be used to conduct exploratory economic analyses separately.

Criteria

Not applicable.

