9.3.2. Safety Analyses

Participants who receive at least 1 dose of study drug will be analyzed for safety. The safety parameters to be evaluated are the incidence, intensity, and type of AEs, vital signs measurements, and clinical laboratory results. Exposure to study drug and reasons for discontinuation of study treatment will be tabulated.

Adverse Events

The verbatim terms used in the eCRF by investigators to identify AEs will be coded using the Medical Dictionary for Regulatory Activities, Version 21.0 or later. and will be graded according to the NCI-CTCAE, Version 4.03. Treatment-emergent AEs are AEs that occur or worsen on or after first dose of study drug through 30 days after the last dose of study drug. All reported intervention-emergent AEs will be included in the analysis. For each AE, the percentage of participants who experience at least 1 occurrence of the given event will be summarized by intervention group. In addition, comparisons between intervention groups will be provided if appropriate.

Treatment-emergent AEs will be summarized by system organ class, preferred term, toxicity grade, and relationship to study drug. Serious adverse events and deaths will also be summarized. Summaries, listings, datasets, or participant narratives may be provided, as appropriate, for those participants who die, who discontinue intervention due to an AE, or who experience a severe or a SAE.

Clinical Laboratory Tests

Laboratory data will be summarized by type of laboratory test. Descriptive statistics will be calculated for each laboratory analyte at baseline and for observed values and changes from baseline at each scheduled time point. A listing of participants with any laboratory results outside the reference ranges will be provided. A listing of participants with any markedly abnormal laboratory results will also be provided. Normal ranges will be used to identify values that are outside the normal ranges and abnormal laboratory results will be graded according to the NCI-CTCAE Version 4.03. A shift summary of baseline grade by maximum post-baseline CTCAE grade will be presented. For each laboratory parameter, the baseline laboratory value will be defined as the last laboratory value collected on or prior to the date of the first dose of study drug. Participants who develop toxicities of Grade ≥3 will be listed.

Electrocardiogram

Electrocardiogram data will be summarized by ECG parameter at screening (baseline) only.

Vital Signs

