6.1. Adverse Events

Subjects will be assessed for adverse events while on the study. Adverse events (AEs) will be graded according to the NCI Common Terminology Criteria for Adverse Events (CTCAE) version 4.03 and coded to preferred term and system organ class (SOC) using the MedDRA version 20.0 or later. All AEs reported on or after the date of first dose until 30 days (inclusive) after the last dose of study drug will be considered treatment-emergent and will be summarized by treatment group.

For each treatment group, AE incidence rates will be summarized with frequency and percentage by SOC and preferred term, with all subjects treated in that treatment group as the denominator, unless otherwise specified. In addition, AE incidence rates will also be summarized by severity and relationship to study drug. Treatment-related AEs are those judged by the Investigator to be at least possibly related to the blinded study drug. AEs with missing severity or relationship to study drug will be classified as severe and treatment-related, respectively. Subjects with multiple occurrences of events will only be counted once at the maximum severity to study drug for each preferred team, SOC. Deaths that occur within 30 days after the last dose of study drug are defined as on-study deaths.

Summary tables of the following AEs will be provided:

Overall summary of AEs: the number and percentage of subjects who experienced any AE including COVID-19, number of subjects with Grade 3/4 AEs, any serious adverse event

22

^b Placebo subjects treated with apalutamide + ADT after cross-over

^c Subjects treated with apalutamide + ADT including subjects from original apalutamide arm and subjects crossed over from placebo arm

(SAE) including COVID-19, any treatment-related AE, treatment related Grade 3/4 AE, any treatment-related SAE, AE leading to treatment discontinuation including COVID-19, related AE leading to treatment discontinuation, AE leading to death including COVID-19, related AE leading to death, and all deaths within 30 days of last dose

- All AEs by SOC and preferred term
- All AEs by SOC, preferred term, and toxicity grade
- Grades 3 or 4 AEs by SOC and preferred term
- Grades 3 or 4 AEs by decreasing frequency of preferred term
- Treatment-related AEs by SOC and preferred term
- Treatment-related AEs by SOC, preferred term, and toxicity grade
- Treatment-related AEs by decreasing frequency of preferred term

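### The 30-day windows for treatment-emergent adverse events and on-study deaths have no rule for new anticancer therapy started inside them, and most such windows fall in the apalutamide columns

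*Protocol*

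**What the plan says.** **Windows.** Protocol 9.3.2 defines treatment-emergent events as those that "occur or worsen on or after first dose of study drug through 30 days after the last dose of study drug". SAP 6.1 agrees: events from first dose "until 30 days (inclusive) after the last dose of study drug will be considered treatment-emergent". It adds: "Deaths that occur within 30 days after the last dose of study drug are defined as on-study deaths". None of the three mentions subsequent therapy.

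**When other anticancer agents may start.** Protocol 6.5.2 makes them "prohibited while on study until the End-of-Treatment Visit or 30 days after last dose of study drug", without saying which limit governs. Protocol 7.1 says men who stop treatment "should complete the EoT Visit within 30 days of the last dose of study drug". The Synopsis says instead: "An End-of-Treatment (EoT) Visit will occur approximately 30 days of the last dose of study treatment". Protocol 4.1, the Schedule of Activities column header and SAP 1.2 match the Synopsis. Protocol 7.1 also lists the start of a subsequent prostate cancer therapy among the reasons to stop study drug. Men with distant metastasis stop study drug and may go on to standard care, with no waiting period stated (Synopsis, Protocol 4.1, SAP 1.2).

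**Efficacy has a rule.** For men given subsequent therapy before PSA progression, "the TTPP will be censored at the last date of PSA assessment prior to the start of subsequent therapy" (Protocol 9.3.1; SAP 5.2.1 is equivalent).

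**Columns.** SAP section 6 reports safety as Placebo (before cross-over only), Apalutamide, Placebo to Apalutamide (after cross-over), and all apalutamide-treated men. Adverse events are given as crude percentages of men treated. No exposure adjustment is planned.

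**The concern.** Safety and tolerability is a secondary objective. A man who stops for metastasis and starts another anticancer drug in the following weeks may have toxicity from the new drug inside the 30 days. It would be counted in the all-cause adverse event, Grade 3/4 and serious event tables of the column he was last treated in, and a death would be counted as on-study. The tables by relationship to study drug give some protection; the all-cause tables give none. SAP 4.6 adds to the difficulty, because it classes medication started up to day 30 after the last dose as concomitant.

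The columns are not equally open to this. A placebo man stays in the Placebo column for at most 5 cycles and, unless he has metastasis, then moves to apalutamide. When he finally stops, his post-treatment window belongs to an apalutamide column. With about 50 men in the apalutamide arm, each event counted this way moves a percentage by 2 points.

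**Working it through.** **1. The plan's own figure.** Protocol 4.2.1 gives 6.2% of placebo men in the global study with metastasis at the first post-baseline scan and no earlier PSA progression, and expects 1-2 such men here. 0.062 x 25 = 1.55, which agrees. These are the main source of post-treatment windows in the Placebo column.

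**2. Apalutamide arm.** Inputs: 50 men; median metastasis-free survival 40.5 months (Protocol 2.2); 32 months of accrual plus 5 of follow-up (Protocol 9.1). Assumed: exponential times and uniform accrual, so follow-up runs from 5 to 37 months. The rate is ln 2/40.5 = 0.01711 per month. The mean proportion stopping is

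1 - (e^(-0.01711 x 5) - e^(-0.01711 x 37))/(0.01711 x 32) = 0.293, or 14.7 of 50.

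Metastasis-free survival includes death, but Protocol Table 1 also gives 40.5 months as the median time to metastasis alone.

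**3. Placebo column, three ways.** Five 28-day cycles are 140/30.4375 = 4.60 months. The global study's placebo medians are 16.2 months for metastasis-free survival and 3.7 months for TTPP, giving rates of 0.0428 and 0.1873 (sum 0.2301).

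- Protocol figure: 6.2%, 1.55 men.
- Exponential model with PSA progression competing: (0.0428/0.2301) x (1 - e^(-0.2301 x 4.60)) = 12.1%, 3.0 men.
- Same model ignoring PSA progression: 1 - e^(-0.0428 x 4.60) = 17.9%, 4.5 men. This is an upper bound, because it keeps every man on placebo for all 5 cycles.

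**4. Men who cross over.** Mean time on placebo is (1 - e^(-0.2301 x 4.60))/0.2301 = 2.84 months. Shortening follow-up by that amount in step 2 gives 25.8%. With 25 x (1 - 0.062) = 23.45 men crossing over, that is 6.0 men. The pooled apalutamide column then has (14.66 + 6.05)/73.45 = 20.7/73.45 = 28%.

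**5. Comparison.**

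| Placebo assumption | Placebo column | Apalutamide arm | Ratio of percents | Ratio of counts |
|---|---|---|---|---|
| Protocol figure | 6.2% | 29.3% | 4.7 | 9.5 |
| Competing risk | 12.1% | 29.3% | 2.4 | 4.8 |
| No competing risk | 17.9% | 29.3% | 1.6 | 3.3 |

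On the protocol figure, 20.7 of 20.7 + 1.55 = 22.3 windows (93%) lie in the apalutamide columns.

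**6. Per person-month on drug.** Apalutamide: exposure is 14.66/0.01711 = 856 person-months, so 1.7 windows per 100. Placebo: 25 x 2.84 = 70.9 person-months, so 1.55/70.9 = 2.2 per 100, or 3.04/70.9 = 4.3 with the competing-risk figure. The direction reverses.

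**7. Effect on Grade 3/4 percentages.** The documents do not give f, the fraction starting new therapy inside the window, or g, the fraction of those with a new Grade 3/4 event in it. I assume f from 0 to 0.75 and g from 0.10 to 0.30.

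- f = 0: no effect in any column.
- f = 0.25, g = 0.10: apalutamide 0.293 x 0.025 = 0.7 points; placebo 0.062 x 0.025 = 0.2 points.
- f = 0.75, g = 0.30: apalutamide 0.293 x 0.225 = 6.6 points; placebo 0.062 x 0.225 = 1.4 points, or 0.179 x 0.225 = 4.0 points on the upper bound.

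**The case against.** The strongest reply is that overlap may hardly occur. Four statements put the End-of-Treatment visit at about 30 days and only Protocol 7.1 says within 30 days. If visits fall near day 30, the two limits in Protocol 6.5.2 nearly coincide and the ban covers almost the whole window. Listing a new therapy as a reason to stop study drug says what follows if it starts; it does not authorise an early start. This stands as to size, and it is why the range begins at zero. It does not close the gap: the word *or* in 6.5.2 is unresolved, and 7.1 is the section that governs men who stop.

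A reader might infer that new-therapy toxicity will count against apalutamide far more often than against placebo, so that the safety comparison is biased in one direction. The documents do not support that. They give no figure for therapy started before day 30. The 4.7 ratio sets a modelled apalutamide figure against an observed first-scan placebo figure; modelling both arms alike lowers it to 2.4, or 1.6 at the bound. The imbalance comes from longer apalutamide exposure and from cross-over, which make every crude percentage unequal, and it is not seen per person-month.

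Two further points stand in part. Existing outputs help with individual cases: events by relationship, deaths by cause, listings, and narratives for serious events and for deaths within 30 days. They do not correct the all-cause tables. And an uncut window is the conservative choice for a safety objective: the effective half-life is 3 days (Protocol 2.2), so drug is still present if new therapy starts early. That argues against replacing the full-window tables, not against showing a second version. The TTPP rule is only a loose parallel, since it serves a hypothetical estimand that safety does not have.

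**Conclusion.** The gap is real and of moderate weight. The plan has no rule for subsequent anticancer therapy inside the 30-day windows, and its own wording leaves room for such therapy. By the final analysis about 29% of apalutamide men would have a window opened by metastasis or death, against 6-18% in the Placebo column. This rests on exponential times, uniform accrual and the global study's medians. Windows opened by stopping for other reasons are not counted.

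The effect on the apalutamide Grade 3/4 percentage lies between about 0 and a few points. The 6.6-point maximum multiplies two extreme inputs that are not in the documents. SAP section 6 plans no safety inference unless otherwise specified, so no test and no part of the primary TTPP conclusion is affected. What is at stake is how clearly the all-cause safety and death tables can be read.

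**What to change.** In SAP 6.1, derive a flag for adverse events and deaths within 30 days of the last dose that occur on or after the start of the first subsequent systemic anticancer therapy. Identify that therapy from the subsequent-therapy record, not from the date rule for concomitant medication in SAP 4.6.

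Present the overall adverse event, Grade 3/4, serious event and on-study death summaries twice: with the full 30-day window, and with the window ended the day before that therapy. In the second version keep any event judged related to study drug. List all flagged events.

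The End-of-Treatment timing in the Synopsis, Schedule of Activities, Protocol 4.1 and SAP 1.2 must be reconciled with Protocol 7.1, and the two limits in Protocol 6.5.2 must be made unambiguous. Which clinical rule applies is for the sponsor to settle.

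The cost is one derived flag and a few extra tables. Subsequent therapy and relationship to study drug are already collected, and the TTPP censoring rule already needs the start dates.

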9.3.3. Other Analyses

Pharmacokinetic Analyses

All plasma concentrations below the lowest quantifiable concentration or missing data will be labeled as such in the concentration data presentations or SAS dataset. Concentrations below the lower quantifiable concentration will be treated as zero in the summary statistics. Participants will be excluded from the PK analysis if their data do not allow for accurate assessment of the PK (eg, incomplete administration of the study drug; missing information of dosing and sampling times). All participants and samples excluded from the analysis will be clearly documented in the Clinical Study Report.

Descriptive statistics including arithmetic mean, SD, geometric mean, coefficient of variation, median, minimum, and maximum will be used to summarize plasma apalutamide and N-desmethyl apalutamide concentrations at each sampling time point.

Mean plasma apalutamide and N-desmethyl apalutamide concentration-time profile will be plotted after the first dose of study intervention. And individual plasma concentration-time profile may also be plotted.

Population PK analysis of plasma concentration-time data of apalutamide and N-desmethyl apalutamide will be performed using nonlinear mixed effects modeling. Details will be given in a population PK analysis plan and the results of the analysis will be presented in a separate report.

Exposure-Response Analyses

Exposure-response analysis between exposure and selective clinical endpoint (eg, incidence of rash) will be explored if deemed necessary and with sufficient data.

